3.4.2.2 Prior aGvHD prophylaxis

The number and percentage of patients who received any aGvHD prophylaxis prior to start of study treatment will be summarized by lowest ATC class, preferred term and group using FAS. Listings will be generated for prophylaxis.

3.4.2.3 Systemic corticosteroid prior to start of study treatment

The number and percentage of patients who received systemic corticosteroids prior to study start will be summarized by age group with number of days on steroids and peak daily dose, where doses of methylprednisolone will be converted to prednisone equivalents. This analysis is done based on Full Analysis Set and will be reported in mg/kg/day (weight adjusted).

3.4.2.4 Systemic corticosteroid during study treatment

Doses of methylprednisolone will be converted to prednisone equivalents by multiplying the methylprednisolone dose by 1.25 and will be reported in mg/kg/day

The duration of exposure will be summarized for systemic corticosteroid by age group. It will also be categorized into time intervals; frequency counts and percentages will be presented for the number (%) of patients in each interval. The actual cumulative dose, dose intensity and

relative dose intensity (relative to the starting dose of corticosteroids) will be summarized up to Day 28, Day 56 and end of on-treatment period.(Section 3.4.1) This analysis will be based on Safety Set. The data will be reported on the Study treatment eCRF through the end of treatment period per EOT Disposition eCRF, and on the Prior and Concomitant Medications eCRF for any data prior and after the end of treatment. The list of systemic corticosteroids will be documented in Data Quality Plan.

3.4.2.5 Calcineurin inhibitors (CNIs) during study treatment

The duration of exposure will be summarized for systemic CNIs (cyclosporine or tacrolimus) up to end of on-treatment period by age group. It will also be categorized into time intervals; frequency counts and percentages will be presented for the number (%) of patients in each interval. These analyses will be based on Safety Set. Data will be analysed similarly to steroids and ruxolitinib as described in section 3.4.1. These data are reported on the study treatment CRF through the end of treatment per EOT Disposition eCRF, and on the Prior and Concomitant Medications eCRF after the end of treatment. The list of CNIs will be documented in the Data Quality Plan.

3.4.2.6 Additional systemic aGvHD therapy

New additional systemic aGvHD therapy (medications and procedures) since start of study treatment will be listed and summarized by lowest ATC class, preferred term, overall and by age group by means of frequency counts and percentages using FAS. These medications will be derived as per Appendix Section 6.4.3. Procedures are not coded by ATC class and hence they will appear under uncoded on the same table.

3.4.2.7 Concomitant medications

Concomitant therapy is defined as all interventions (therapeutic treatments, blood component transfusions and procedures) other than the study treatment administered to a patient coinciding with the study treatment period. Concomitant therapy include medications (other than study drugs) starting on or after the start date of study treatment or medications starting prior to the start date of study treatment and continuing after the start date of study treatment.

Concomitant medications will be coded using the World Health Organization (WHO) Drug Reference Listing (DRL) dictionary that employs the WHO Anatomical Therapeutic Chemical (ATC) classification system and summarized by lowest ATC class and preferred term using frequency counts and percentages. Surgical and medical procedures will be coded using MedDRA and summarized by SOC and preferred term. The summaries using Safety Set will include:

- Medications starting on or after the start of study treatment but no later than end of on-treatment period; and
- Medications starting prior to start of study treatment and continuing after the start of study treatment.

All concomitant therapies will be listed using Safety Set. Any concomitant therapies starting and ending prior to the start of study treatment or starting beyond end of on-treatment period will be flagged in the listing.

All concomitant CYP3A4 inhibitors and type of blood component transfusions will be summarized by ATC class and preferred term based on Full analysis Set.

3.5 Analysis of the primary objective

The primary objective of the Phase I is to assess pharmacokinetic (PK) parameters of ruxolitinib for patients with aGvHD and SR-aGvHD and define an age appropriate RP2D for each of the groups 2-4. The primary objective of the Phase II is to measure the activity of ruxolitinib in patients with aGvHD or SR-aGvHD assessed by Overall Response Rate (ORR) at Day 28.

3.5.1 Primary endpoint

The primary endpoint of the Phase I is the list of following PK parameters (AUC, Cmax, T1/2, Ctrough, and other parameters, as appropriate) which will be derived using non-compartmental methods in subjects with extensive sampling (Groups 1, 2, and 3). These parameters will then be used to define a RP2D for Groups 2, 3, and 4. The observed PK parameters (within group) will be summarized and compared to information obtained from adult and adolescent aGvHD patients treated with ruxolitinib on study CINC424C2301. Data from patients older than 2 years old will be combined and analyzed by PBPK methods to determine the dose to be administered in patients younger than 2 years old (Group 4).

The primary endpoint for the Phase II is the investigator-reported overall response rate (ORR) at Day 28, defined as the proportion of patients with complete response (CR) or partial response (PR) without requirement for additional systemic therapies for an earlier progression, mixed response or non-response as per [Table 8-3](#) of the protocol ([Harris et al 2016](#)). Note that response is relative to the assessment of aGvHD at the start of study treatment.

- **Complete-response** is defined as a score of 0 for the aGvHD grading in all evaluable organs that indicates complete resolution of all signs and symptoms of aGvHD in all evaluable organs without administration of additional systemic therapies for any earlier progression, mixed response or non-response of aGvHD.
- **Partial response** is defined as improvement of 1 stage in 1 or more organs involved with aGvHD signs or symptoms without progression in other organs or sites without administration of additional systemic therapies for an earlier progression, mixed response or non-response of aGvHD.
- **Lack of response** is defined as no response, mixed response, or progression.
- **No response** is defined as absence of improvement in any organ involved by aGvHD, without worsening in any involved organ.
- **Mixed response** is defined as improvement of at least 1 stage in the severity of aGvHD in at least one organ accompanied by progression in another organ or development of signs or symptoms of aGvHD in a new organ.
- **Progression** is defined as worsening in 1 or more organs by 1 or more stages without improvement in any involved organ

Patients requiring additional systemic therapy for aGvHD will be classified as non-responders, and patients with missing baseline or Day 28 aGvHD response assessment will be considered as treatment non-responders.

aGvHD Flare is defined as any increase in signs or symptoms of aGvHD that is sustained for >24h after an initial response (CR or PR) and requires re-escalation of immunosuppressive therapy (e.g. corticosteroid, CNI and/or ruxolitinib dosing). While all aGvHD flares will be captured on study whether occurring during steroid, CNI or ruxolitinib taper. Only flares in GvHD that require new additional systemic therapy, will be considered aGvHD flare failure.

Acute GvHD will be assessed as per [Table 8-2](#) of the protocol. Grade will be calculated based on the staging of the organs and recorded on the eCRF by the Investigator. The Investigator reported grade will be used for all analyses. Grade and response will be calculated by the sponsor for the purposes of data review.

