6.4 Treatment blinding

This is an open-label study. Therefore, treatment will be open to patients, investigator staff, persons performing the assessments, and the Clinical Trial Team (CTT).

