Patients requiring additional systemic therapy for aGvHD will be classified as non-responders, and patients with missing baseline or Day 28 aGvHD response assessment will be considered as treatment non-responders.

aGvHD Flare is defined as any increase in signs or symptoms of aGvHD that is sustained for >24h after an initial response (CR or PR) and requires re-escalation of immunosuppressive therapy (e.g. corticosteroid, CNI and/or ruxolitinib dosing). While all aGvHD flares will be captured on study whether occurring during steroid, CNI or ruxolitinib taper. Only flares in GvHD that require new additional systemic therapy, will be considered aGvHD flare failure.

Acute GvHD will be assessed as per [Table 8-2 \(Harris et al 2016\)](#). Grade will be calculated based on the staging of the organs and recorded on the eCRF by the Investigator. The Investigator reported grade will be used for all analyses. Grade and response will be calculated by the sponsor for the purposes of data review and sensitivity analysis.

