12.4.4 Sensitivity and Supportive analyses

As supportive analyses, the estimate of response rates ORR at Day 28 will be presented by diagnosis (treatment naïve aGvHD and SR-aGvHD) on the EES.

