3.5.4 Supportive analyses

The subgroup analyses to assess the homogeneity of the treatment effect across demographic and baseline disease characteristics will be performed on the EES as appropriate. The subgroups are described in section 2.2.1.

A sensitivity analysis excluding subjects who had protocol deviations of organ staging or aGvHD response assessments not strictly following standard criteria defined in study protocol (PDID: OTHER03, OTHER04 per ECS) at Day 28 will be conducted.

Efficacy analyses in subgroups will be purely exploratory and are intended to explore the consistency of treatment effect. No inferential statistics (p-values) will be produced for the subgroups.

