Sample size	Minimum No. of responders	Response Rate	Probability to have a 90% CI with lower limit $\geq 60\%$	90% CI	
37	28	0.76	0.809	0.614	0.867
38	29	0.76	0.784	0.623	0.871
39	29	0.74	0.859	0.604	0.854
40	30	0.75	0.839	0.613	0.858
41	31	0.76	0.818	0.621	0.861
42	31	0.74	0.882	0.604	0.846
43	32	0.74	0.864	0.612	0.849
44	33	0.75	0.846	0.620	0.853
45	33	0.73	0.901	0.604	0.838
46	34	0.74	0.886	0.612	0.842
47	35	0.74	0.869	0.619	0.846
48	35	0.73	0.916	0.604	0.832
49	36	0.73	0.903	0.612	0.835
50	37	0.74	0.889	0.619	0.838

5 Change to protocol specified analyses

No change from protocol

6 Appendix

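### The SAP drops, without declaring it, the protocol's sensitivity analysis on sponsor-calculated response, and the exclusion analysis in SAP 3.5.4 only partly covers the gap

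*SAP*

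**What the plan says.** Protocol 12.4.1, which defines the primary endpoint, gives the sponsor's calculation two uses: "Grade and response will be calculated by the sponsor for the purposes of data review and sensitivity analysis". SAP 3.5.1 carries the same paragraph, but its sentence ends sooner: "Grade and response will be calculated by the sponsor for the purposes of data review".

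The SAP defines the endpoint by its source: "The primary endpoint for the Phase II is the investigator-reported overall response rate (ORR) at Day 28". It adds: "The Investigator reported grade will be used for all analyses". The protocol has that second sentence too, but there the sensitivity use that follows qualifies it. In the SAP nothing does.

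Two sections deal with supporting analyses of the primary endpoint:

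- Protocol 12.4.4 contains only this: "As supportive analyses, the estimate of response rates ORR at Day 28 will be presented by diagnosis (treatment naïve aGvHD and SR-aGvHD) on the EES".
- SAP 3.5.4 plans subgroup analyses and one sensitivity analysis: "A sensitivity analysis excluding subjects who had protocol deviations of organ staging or aGvHD response assessments not strictly following standard criteria defined in study protocol". It applies at Day 28 and relies on deviation codes OTHER03 and OTHER04. SAP section 1 records that it was added in SAP amendment 1.

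SAP section 5, where departures from the protocol's analyses belong, says "No change from protocol".

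**The concern.** The trial is single-arm and, under Protocol 6.4, those who assess the patients know the treatment. The primary result is one proportion built from investigators' response calls, so how those calls follow from the recorded organ stages deserves a check. The SAP accepts that calls may depart from the criteria, since it holds deviation codes for that.

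The documents also leave room for different calls. Protocol Table 8-3 scores response against organ stage at both screening and Day 1, while Protocol 12.4.3 and SAP 3.5.3 take the last assessment at or before the start of treatment as baseline. One algorithm applied to every patient's recorded stages would show how far such differences move ORR.

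If the SAP is followed as written, the sponsor calculates that response but need not report an ORR from it. A reader of section 5 would also believe that nothing in the protocol had been dropped.

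**Working it through.** **Step 1: the text.**

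| Item | Protocol | SAP |
|---|---|---|
| Use of sponsor-calculated grade and response | Data review and sensitivity analysis (12.4.1) | Data review only (3.5.1) |
| ORR from sponsor-derived response specified | Not in 12.4.4 | Not in 3.5.4 or any other visible section |
| Change declared | – | None (section 5) |

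The amendment summaries in SAP section 1, as far as they can be read, do not mention the removal. SAP amendment 3 says that it aligns with protocol amendment 3, and that is the protocol version that still carries the commitment.

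**Step 2: the plan's own figure.** Inputs from SAP section 4: N = 45, true ORR 80%, two-sided 90% Clopper-Pearson interval, target lower limit at least 60%. For x responders among n patients,

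lower limit = 5th percentile of Beta(x, n − x + 1); upper limit = 95th percentile of Beta(x + 1, n − x).

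The smallest x with a lower limit of at least 0.60 at n = 45 is 33, with interval 0.604 to 0.838. P(X ≥ 33 | n = 45, p = 0.80) = 0.9005, against 0.901 stated. The plan's figure reproduces.

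**Step 3: is the exclusion analysis equivalent?** Assume 36/45 = 80.0% investigator-reported responders, and that k of them are not responders by the sponsor's calculation. Both numbers are assumptions. Reclassification gives (36 − k)/45; exclusion gives (36 − k)/(45 − k).

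| k | Reclassified | 90% lower limit | Excluded | 90% lower limit |
|---|---|---|---|---|
| 0 | 36/45 = 80.0% | 0.677 | 36/45 = 80.0% | 0.677 |
| 1 | 35/45 = 77.8% | 0.652 | 35/44 = 79.5% | 0.670 |
| 2 | 34/45 = 75.6% | 0.628 | 34/43 = 79.1% | 0.663 |
| 3 | 33/45 = 73.3% | 0.604 | 33/42 = 78.6% | 0.656 |
| 4 | 32/45 = 71.1% | 0.580 | 32/41 = 78.0% | 0.648 |
| 6 | 30/45 = 66.7% | 0.534 | 30/39 = 76.9% | 0.632 |

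Each reclassified patient moves ORR by 1/45 = 2.2 points. Four exclusions together move it by 80.0 − 78.0 = 2.0 points, against 80.0 − 71.1 = 8.9 for four reclassifications. At k = 4 the two analyses fall on opposite sides of 60%.

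That split depends on the starting count. From the minimum of 33/45 (lower limit 0.604), one reclassification gives 32/45 (0.580) and one exclusion gives 32/44 (0.596), both below 60%.

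The table also assumes that all k patients carry a deviation code. Any who do not would stay in the exclusion analysis as responders.

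**The case against.** A reader might infer that the investigator's call is now never tested, or that the sponsor's calculation was the only check on it. The documents do not support that. SAP 3.5.4 plans a sensitivity analysis aimed at staging and response calls that depart from the criteria, and it was added on purpose.

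A reader might also infer that restoring the analysis would expose open-label bias. It would not. The documents describe no independent or blinded organ assessment, so the sponsor would presumably start from the investigator's own stages (the derivation is not specified). Such a calculation finds errors in turning stages into response, not optimistic staging.

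Three further objections have weight:

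- The protocol's commitment is a closing phrase. It names no time point, population or method, and 12.4.4 does not list the analysis. This makes the commitment thin, but it is explicit and sits in the primary-endpoint section, and the SAP is where it should have been worked out.
- The counts are hypothetical and run one way; recalculation could also turn non-responders into responders. From 36/45 it takes a net four of 36 responders (11%) to pass below 60%, and three leave 0.604. SAP 3.14 says that no efficacy hypothesis is tested, so crossing 60% changes no planned conclusion.
- The sponsor still calculates response for data review, and Protocol 11.2 provides for queries on discrepancies. Mismatches may well be settled before database lock, although the documents do not say so. If they are, a concordance table would show it.

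These points limit how much the omission matters. They leave both the textual discrepancy and the incorrect statement in section 5 in place.

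**Conclusion.** The point holds as an undeclared departure of the SAP from the protocol. A sensitivity use of sponsor-calculated response was removed, no sponsor-derived ORR replaces it, and section 5 is wrong to report no change. The textual part is certain.

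The exclusion analysis is a partial check and not a substitute: it depends on deviations having been coded, and it removes patients from numerator and denominator where a recalculation would reclassify them. In the illustration the lower limits are 0.648 and 0.580 for the same four patients. That rests on an assumed 36/45, an assumed four discordant calls all in one direction, and all four being coded as deviations. The 60% limit serves only sizing.

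The primary estimate remains valid as defined, and no sample size or probability changes. What is lost is a check on how response is derived from the investigator's stages. The point should be corrected, but it does not undermine the design.

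**What to change.** In SAP 3.5.1, restore the words *and sensitivity analysis*. In SAP 3.5.4, add:

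1. Day 28 ORR from sponsor-derived response, calculated from the recorded organ stages, on the full EES denominator with an exact two-sided 90% CI. State the derivation rule, including which assessment serves as baseline.
2. A table of investigator against sponsor response at Day 28.

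State beside them that they test how response is derived from the investigator's stages and do not address bias in the staging. Keep the exclusion analysis. A sponsor-derived durable ORR at Day 56 is an optional extension that goes beyond the protocol's wording.

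If the sponsor prefers not to restore the analysis, section 5 must declare the removal and give the reason.

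Cost: one or two extra tables from values already calculated for data review, with no new data and no change to the sample size.

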3.5.2 Statistical hypothesis, model, and method of analysis

Pharmacokinetic parameters for patients in Groups 1, 2, 3 and 4 (who are part of the PAS) will be compared to adult information from study [\[CINC424C2301\]](#) through the use of ANOVA methods. The geometric mean ratio with 90% CI will be provided.

The response rates for ORR at Day 28 will be estimated on the Efficacy Evaluable Set (EES). Two-sided 90% confidence intervals [\[Clopper and Pearson 1934\]](#) will be calculated based on the exact method for binomial distribution. Summary statistics (frequencies and percentages) will be provided.

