3.1.1 Determination of recommended Phase II dose

- Group 2 (age ≥6y to <12y) and Group 3 (age ≥2y to <6y): Physiologically based pharmacokinetic (PBPK) modeling will be used to derive a starting dosing for these patients, which is predicted to yield an exposure equivalent to that of a 10 mg BID in adults. The PBPK model will incorporate PK data from adult and adolescent patients with SR-aGvHD treated on study [CINC424C2301], and these predictions will be compared to existing data in pediatric patients from other indications (Loh et al 2015). The starting doses are thereby assigned as 5 mg BID (Group 2) and 4 mg/m² BID (Group 3).
- Group 4 (≥ 28 days to < 2 y): the absence of existing ruxolitinib PK data in this age group warrants a conservative approach. Therefore, the starting dose for Group 4 will be determined by using PK data generated in Groups 1, 2 and 3 (Table 3-1 and Table 3-2). These data will be used to inform the PBPK model in order to enable accurate predictions for these very young patients.

Groups 2 and 3 will enroll a minimum of 5 patients each. Full ruxolitinib concentration-time courses, safety and activity data will be collected over 28 days. Should one or more of the 5 patients not be evaluable, or until the dose/exposure is confirmed, additional patients may be enrolled to ensure a minimum of 5 evaluable patients per age group. This information will be used to assess the adequacy of this preliminary dose, which can be adapted if needed (e.g. to account for any potential difference between the expected and the observed ruxolitinib exposure).

If the exposure from the first 5 patients does not approximate the exposure of 10mg BID in adult and adolescent patients based on AUC and Cmax, at least an additional group of 5 patients will be enrolled in that specific age group. This second group of at least 5 patients may be administered a different starting dose to again target the 10mg BID adult exposure. This process will continue until the dose-exposure relationship is confirmed (i.e. selection of the RP2D for those ages based on exposure and safety review by the DMC). If the selected RP2D is higher than the starting dose assigned to the previous group of patients, intra-patient dose escalation is allowed ([Section 6.5.1.1](#)). Inversely, if the selected RP2D is lower than the starting dose assigned to the previous group of patients, intra-patient dose de-escalation is allowed.

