12.8 Sample size calculation

12.8.1 Primary endpoint(s)

In Phase I, 5 patients will be enrolled to each age group with no minimum for Group 4. A minimum of 5 patients in Group 1 will also undergo extensive PK sampling during Phase II. Should one or more of the 5 patients not be evaluable for PK analysis, additional patients may be enrolled to ensure a minimum of 5 evaluable PK profiles for Groups 1, 2 and 3.

A comparison of PK parameters (Cmax) from 5 pediatric patients (in Groups 2 and 3 separately) to ~25 adult patients (from study [\[\[CINC424C2301\]\]](#)) will be performed. With expected similarity in the point estimates across groups (geo-mean ratio, GMR = 1), and accounting for expected higher variability in the pediatric patients (CV% ~55.7%, [\(Loh et al 2015](#), detailed data on file) compared to ~40% in adults), the confidence interval for a GMR of 1 would be [0.609;1.641] which demonstrates clinically relevant comparability of exposure to adult exposure (within 2-fold).

Therefore, with a minimum of 5 evaluable profiles in each of Groups 2 and 3, combined with 5 evaluable profiles from Group 1 and further sparse PK samples in the Phase II of the study, there is sufficient precision to support the PK objectives of the study.

Should the exposure in Group 2, 3 or 4 not be confirmed following the PK sampling in at least 5 patients, additional patients will be enrolled in that specific age group until the dose/exposure is confirmed (i.e., selection of the RP2D for those ages based on exposure and safety review by the DMC). Once the RP2D is selected for Groups 2 and 3 any further eligible patients between the ages of 2 years and 12 years will be enrolled into the Phase II, and Group 4 will begin enrolling patients in the Phase I.

Although several studies of treatments for aGvHD and SR-aGvHD have included pediatric patients, it is difficult to find recent estimates for steroid response in de novo aGvHD pediatric patients or BAT response in SR-aGvHD pediatric patients. A review of 443 patients (including 175 patients < 20 years), reported a CR/PR rate of 55% at Day 28, no association with ORR rate and patient age was found ([MacMillan et al 2010](#)). Other papers report response rates in the ranges 50-60% for de novo and SR-aGvHD ([Martin et al 2012](#)).

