3.14 Interim analysis

No formal interim analysis is planned for this study. However, summaries of safety and PK data will be produced to support the regular safety monitoring conducted by the DMC and the confirmation of RP2D. Efficacy data may also be analyzed when all patients (Phase I and Phase II) have completed 24 weeks (approximately 6 months) of treatment or discontinued earlier. The final analysis will be conducted when all patients have completed Month 24 (i.e., the end of the long-term follow-up period), unless the patients discontinue earlier.

In this clinical trial it is not planned to test specific efficacy hypotheses but to provide estimates of efficacy endpoints for the pediatric study population and therefore no-alpha adjustment will be made for earlier estimates of efficacy endpoints. However, the data for the primary efficacy assessment, ORR at Day 28 will already be final once all patients have completed 6 months of treatment.

4 Sample size calculation

In Phase I, 5 patients will be enrolled to each age groups 2 and 3. A minimum of 5 patients in Group 1 will also undergo extensive PK sampling during Phase II. Should one or more of the 5 patients not be evaluable for PK analysis, additional patients may be enrolled to ensure a minimum of 5 evaluable PK profiles for Groups 1, 2 and 3.

A comparison of PK parameters (Cmax) from 5 pediatric patients (in Groups 2 and 3 separately) to ~25 adult patients (from study CINC424C2301) will be performed. With expected similarity in the point estimates across groups (geo-mean ratio, GMR = 1), and accounting for expected higher variability in the pediatric patients (CV% ~55.7%, ([Loh et al 2015](#), detailed data on file) compared to ~40% in adults), the confidence interval for a GMR of 1 would be [0.609;1.641] which demonstrates clinically relevant comparability of exposure to adult exposure (within 2-fold).

Therefore, with a minimum of 5 evaluable profiles in each of Groups 2 and 3, combined with 5 evaluable profiles from Group 1 and further sparse PK samples in the Phase II of the study, there is sufficient precision to support the PK objectives of the study.

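### The PK comparison with adults leaves the ANOVA variance structure unstated; pooling would give a Cmax 90% CI covering about 82% at the planning inputs, and it is not the model behind the interval that justifies five children per group

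*SAP*

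**What the plan says.** The analysis text is the same in protocol 12.4.2 and SAP 3.5.2. PK parameters are compared with adult data from study CINC424C2301 "through the use of ANOVA methods. The geometric mean ratio with 90% CI will be provided". Neither document gives the variance structure or the degrees of freedom. SAP 3.9 covers non-compartmental parameters and descriptive statistics. SAP 6.4 covers confidence intervals for response rates and the definition of new systemic therapy.

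The precision claim is in protocol 12.8.1 and SAP section 4. It concerns "A comparison of PK parameters (Cmax) from 5 pediatric patients (in Groups 2 and 3 separately) to ~25 adult patients", with a true ratio of 1, a CV of about 55.7% in children and about 40% in adults. It is described as "accounting for expected higher variability in the pediatric patients". The result is stated as: "the confidence interval for a GMR of 1 would be [0.609;1.641" (upper limit 1.641). Both documents read this as comparability within 2-fold and conclude that precision is sufficient.

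The dose decision is worded separately. Under protocol 3.1.1, more patients are enrolled if exposure "does not approximate the exposure of 10mg BID in adult and adolescent patients based on AUC and Cmax", and the data monitoring committee reviews exposure and safety.

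**The concern.** The planning text expects children to be more variable than adults, and the pediatric group is the small one. In that configuration a pooled variance is a poor choice: the 25 less variable adults dominate the variance estimate, which is then applied to a mean from five more variable children. The standard error comes out too small and the interval too narrow.

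PK parameters are the Phase I primary endpoint, and this ratio with its interval is their planned comparison with adults. If the analyst takes ANOVA in its ordinary sense, the reported intervals would be labelled 90% but cover less, and they would not be the kind of interval on which the choice of five patients rests. With the model unstated, two analysts could report materially different precision from the same data.

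**Working it through.** **Inputs** (protocol 12.8.1 and SAP section 4): 5 children, about 25 adults, CV 55.7% and 40%, ratio 1, Cmax. The 90% level comes from protocol 12.4.2 and SAP 3.5.2, because the sample-size text gives no level.

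**Log-scale variances**, v = ln(1 + CV²):
- children: ln(1 + 0.557²) = 0.2702
- adults: ln(1 + 0.40²) = 0.1484

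**Reproducing the plan's interval (Welch).**
- SE = √(0.2702/5 + 0.1484/25) = √0.05998 = 0.2449
- Satterthwaite df = 0.05998² / [(0.2702/5)²/4 + (0.1484/25)²/24] = 4.92
- t(0.95; 4.92) = 2.0226, log half-width = 0.4953
- 90% CI = 0.6094 to 1.6411, which matches the stated figure.

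**Other forms tried.**
- Unequal-variance SE with a normal quantile: 0.668 to 1.496 at 90%, 0.619 to 1.616 at 95%.
- The same SE with t on 28 df: 0.659 to 1.517 at 90%, 0.606 to 1.651 at 95%.
- The same SE with t on 4 df: 0.593 to 1.686 at 90%, 0.507 to 1.974 at 95%.
- Pooled at 95%: 0.665 to 1.505.
- One-sample t on the five children alone, adult mean taken as fixed: SE = √(0.2702/5) = 0.2325, t(0.95; 4) = 2.1318, giving 0.6092 to 1.6415 (1.64148 before rounding).

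Of these, only the one-sample form also rounds to the stated interval. It does not use the adult number and CV that the text lists, so Welch is the reading that fits the comparison described. Neither is a pooled ANOVA.

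**Pooled ANOVA, one pediatric group against adults.**
- Pooled variance = (4 × 0.2702 + 24 × 0.1484)/28 = 0.1658
- SE = √(0.1658 × (1/5 + 1/25)) = 0.1995
- t(0.95; 28) = 1.7011, log half-width = 0.3394
- 90% CI = 0.712 to 1.404; 1 − 0.3394/0.4953 = 31% narrower.

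**Pooled ANOVA, three pediatric groups of five (all at CV 55.7%) with 25 adults.**
- Pooled variance = (12 × 0.2702 + 24 × 0.1484)/36 = 0.1890
- SE = 0.2130, 36 df, log half-width = 0.3596
- 90% CI = 0.698 to 1.433, 27% narrower.

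**Coverage of the nominal 90% interval**, simulated from normal log-scale data (400,000 or more datasets per scenario):

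| Scenario | Pooled coverage |
|---|---|
| 5 v 25, CV 55.7% v 40% | 82% (Welch 89%) |
| Three pediatric groups in one model | 85% |
| 20 adults / 30 adults | 83% / 82% |
| Pediatric CV 40% | 90% |
| Pediatric CV 45% / 50% / 70% | 87% / 85% / 77% |
| 10 pediatric profiles | 85% |
| 12 / 15 pediatric profiles | 86% / 87% |

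The last row is an upper bound: it supposes that all 12 Group 2 or all 15 Group 3 patients enrolled had full profiles.

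**The case against.** **The documents do not say that variances are pooled.** This is right. A model with group-specific variances is compatible with the wording and with a sample-size text that expects unequal variability. A reader might infer that the plan commits to an interval with 82% coverage. It does not: the defect is an unstated choice whose ordinary reading has that consequence.

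**The method behind the planning interval is not established.** This also stands. A reader might take Welch as proven, but the documents name neither method nor confidence level, and the one-sample form rounds to the same figures. What survives is that neither candidate is a pooled interval.

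**The model may be specified elsewhere.** SAP section 1, in its account of SAP amendment 1, sends some PK analysis to a separate SAP and report. Whether that covers the adult comparison cannot be told from these documents. The population PK plan mentioned in SAP 3.9 is for a different analysis.

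**Dose selection is untouched.** A reader might infer that the RP2D is at risk. The documents do not support that: protocol 3.1.1 and 6.5.1 rest confirmation on exposure approximating that of adults and on committee review, with no rule based on a confidence limit. At an observed ratio of 1 and the planning CVs, both the Welch and the pooled interval lie within 2-fold.

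**Five is a minimum, and the size depends on the CVs.** Correct, as the table shows.

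**Group 4.** The ANOVA sentence names Groups 1 to 4, while the parameters are "derived using non-compartmental methods in subjects with extensive sampling (Groups 1, 2, and 3"). A reader might count this as a second defect. It is moot: the Amendment 3 rationale reports completed enrollment of 18 + 12 + 15 = 45 patients in Groups 1 to 3, so no Group 4 comparison can arise.

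**Conclusion.** The point holds as an under-specification with a measurable consequence. If variances are pooled, the Cmax interval at the plan's own inputs would be 0.712 to 1.404 instead of 0.609 to 1.641. Its coverage would be about 82% for one group of five against 25 adults, or about 85% when three such groups share a model, against 89% for Welch.

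These figures assume log-normal Cmax, the planning CVs and exactly five profiles per group. They apply to Cmax only, because the documents give no planning CVs for AUC, half-life or trough concentration. The harm is limited to reported precision and its consistency with the sample-size section. The change is worth making because it concerns the Phase I primary endpoint and costs little.

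**What to change.** In protocol 12.4.2 and SAP 3.5.2, replace the reference to ANOVA methods with a linear model on log-transformed parameters, with group-specific variances and Satterthwaite degrees of freedom, comparing each pediatric group that has non-compartmental profiles (Groups 1 to 3) with adults. If the separate PK SAP already specifies this, a cross-reference is enough. In protocol 12.8.1 and SAP section 4, label the planning interval as an expected 90% unequal-variance interval at an observed ratio of 1, if that is how it was derived.

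No new data are needed. The cost is wider intervals whose width varies more, because the pediatric variance rests on 4 degrees of freedom. In simulation at the planning inputs, the upper limit centred on a ratio of 1 ran from 1.25 to 2.14 (5th to 95th percentile) with Welch, against 1.30 to 1.51 pooled. With a true ratio of 1, the whole interval fell within 2-fold in 58% of datasets with Welch and 85% pooled. The report should expect that, and should not read the stated 0.609 to 1.641 as a guaranteed width.
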